## 9. Balance Assessment after PS matching

Action report name:

- For Liraglutide vs 2nd Gen. SUs

Optum: <https://bwh-dope.aetion.com/projects/details/632/results/44783/result/0>

Marketscan: <https://bwh-dope.aetion.com/projects/details/633/results/45436/result/0>

Medicare: <https://bwh-dope.aetion.com/projects/details/634/results/45432/result/0>

- For Liraglutide vs DPP4i

Optum: <https://bwh-dope.aetion.com/projects/details/632/results/44786/result/0>

Marketscan: <https://bwh-dope.aetion.com/projects/details/633/results/44787/result/0>

Medicare: <https://bwh-dope.aetion.com/projects/details/634/results/45433/result/0>

Date conducted: 11/18/2019 (Medicare 11/30/2019)

After review of initial feasibility and power analyses, complete creation of the remaining covariates (see Table 1 below for list of covariates). Again, using the dummy outcome of a 90-day gap in database enrollment, complete a 1:1 PS-matched analysis. The PS should include the complete list of covariates (excluding laboratory values, which are missing in some patients).

- Provide plot of PS distributions stratified by treatment group.

Note- Please refer to **Appendix B**.

- Report covariate balance after matching.

Note- For Table 1, please refer to **Appendix B**.

- Report reasons for censoring by treatment group.

- For Liraglutide vs DPP4i

	Overall	Referent	Exposure
Dummy Outcome	0 (0.00%)	0 (0.00%)	0 (0.00%)
Death	1,271 (0.75%)	827 (0.98%)	444 (0.53%)
Start of an additional exposure	4,700 (2.79%)	1,913 (2.27%)	2,787 (3.30%)

End of index exposure	99,981 (59.27%)	45,078 (53.44%)	54,903 (65.09%)
Specified date reached	29,951 (17.76%)	16,708 (19.81%)	13,243 (15.70%)
End of patient enrollment	22,798 (13.51%)	12,483 (14.80%)	10,315 (12.23%)
Switch to other SUs (for censoring) + nursing home admission	9,989 (5.92%)	7,336 (8.70%)	2,653 (3.15%)

- For Liraglutide vs 2nd Gen. SUs

	Overall	Referent	Exposure
Dummy Outcome	0 (0.00%)	0 (0.00%)	0 (0.00%)
Death	858 (0.79%)	595 (1.10%)	263 (0.49%)
Start of an additional exposure	4,294 (3.96%)	967 (1.78%)	3,327 (6.14%)
End of index exposure	61,038 (56.33%)	27,098 (50.01%)	33,940 (62.64%)
Specified date reached	21,830 (20.15%)	13,222 (24.40%)	8,608 (15.89%)
End of patient enrollment	14,181 (13.09%)	7,902 (14.58%)	6,279 (11.59%)
Switch to other SUs (for censoring) + nursing home admission	6,163 (5.69%)	4,398 (8.12%)	1,765 (3.26%)

- Report follow-up time by treatment group.

- For Liraglutide vs DPP4i

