5	An acute coronary or cerebrovascular event in the previous 14 days	Measured 14 days prior to drug initiation in any diagnosis/procedure position and inpatient care setting MI, stroke, revascularization, PTCA, CABG: Acute MI ICD-9 diagnosis 410.xx Coronary revascularization-PTCA: Inpatient CPT-4: 92973, 92982, 92984, 92995, 92996, 92920 – 92921, 92924 – 92925, 92937, 92938, 92941, 92943, 92944 – OR – Inpatient ICD-9 procedure: 00.66, 36.01, 36.02, 36.03, 36.05, 36.09 Stenting: Inpatient CPT-4: 92980, 92981, 92928 – 92929, 92933 – 92934 – OR – Inpatient ICD-9 procedure: 36.06, 36.07 Transmyocardial revascularization CPT-4: 33140, 33141 – OR – Inpatient ICD-9 procedure: 36.31-36.34 CABG: Inpatient CPT-4: 33510 – 33536, 33545, 33572 – OR – Inpatient ICD-9 procedure: 36.1x, 36.2x Stroke ICD-9 diagnosis: 430.xx Subarachnoid hemorrhage (SAH) 431.xx Intracerebral hemorrhage (ICH) 433.x1 Occlusion and stenosis of precerbral arteries with cerebral infarction 434.x1 Occlusion and stenosis of cerebral arteries with cerebral infarction 436.x Acute, but ill-defined cerebrovascular events	
6	Currently planned coronary, carotid or peripheral artery revascularization	N/A	
7	Chronic heart failure NYHA class IV	Measured 180 days prior to drug initiation in any diagnosis/procedure position and inpatient or outpatient care setting Oxygen use codes: HCPCS: E0424 E0425 E0430 E0431 E0433 E0434 E0435 E0439 E0440 E0441 E0442 E0443 E0444 E0447 E1390 E1391 E1392 E1405 E1406 K0738 S8120 S8121 or ICD-10 : Dependence on Supplemental oxygen Z99.81 ICD-9: Other dependence on machines, supplemental oxygen V46.2	
ORIGINAL DEFINITION: Inpatient Heart failure (CHF) in prior 60 days Any of ICD-9 codes : 428.x, 398.91, 402.01, 402.11, 402.91, 404.01, 404.11, 404.91, 404.03, 404.13, 404.93
 
NEW DEFINITION 4/22/2019: Inpatient diagnosis may not be specific enough for including severe symptomatic class IV patients. Therefore, we decided to incorporate the use of oxygen therapy (not limited to inpatient setting).

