...median (IQR)	4.00 [0.00, 9.00]	5.00 [0.00, 10.00]	-0.12	0.00 [0.00, 4.00]	0.00 [0.00, 4.00]	0.00	3.00 [0.00, 9.00]	3.00 [0.00, 10.00]	0.00	2.60 (8.84)	2.72 (7.76)
Use of thiazide; n (%)	19,082 (13.9%)	2,749 (14.1%)	-0.005763928	18,570 (13.0%)	2,811 (13.4%)	-0.01181737	66,785 (14.7%)	6,981 (15.6%)	-0.02510409	104,437 (14.2%)	12,541 (14.7%)
Use of beta blockers; n (%)	62,221 (45.2%)	8,804 (45.2%)	0.00	67,518 (47.1%)	9,653 (45.9%)	0.02	233,117 (51.3%)	21,826 (48.7%)	0.05	362,856 (49.3%)	40,283 (47.2%)
Use of calcium channel blockers; n (%)	46,524 (33.8%)	5,822 (29.9%)	0.08	46,777 (32.6%)	6,355 (30.2%)	0.05	167,449 (36.8%)	14,468 (32.3%)	0.09	260,750 (35.4%)	26,645 (31.2%)

Table 1: Liraglutide vs DPP4i

PS-matched												
	Optum		MarketScan		Medicare		POOLED					
Variable	Reference-DPP4i 19187	Exposure- Liraglutide 19187	St. Diff.	Reference-DPP4i 20777	Exposure- Liraglutide 20777	St. Diff.	Reference-DPP4i 44381	Exposure- Liraglutide 44381	St. Diff.	Reference-DPP4i 84,345	Exposure- Liraglutide 84,345	St. Diff.
Number of patients												
Age												
...mean (sd)	65.88 (7.35)	66.08 (6.82)	-0.03	62.98 (6.89)	63.12 (6.32)	-0.02	70.54 (5.22)	70.62 (5.01)	-0.02	67.62 (6.19)	67.74 (5.80)	-0.02
...median [IQR]	66.00 [61.00, 70.00]	66.00 [61.00, 70.00]	0.00	62.00 [60.00, 66.00]	62.00 [60.00, 66.00]	0.00	69.00 [67.00, 73.00]	69.00 [67.00, 73.00]	0.00	66.59 (6.19)	66.59 (5.80)	0.00
Age categories												
...18 - 54; n (%)	1,284 (6.7%)	1,036 (5.4%)	0.05	2,089 (10.1%)	1,724 (8.3%)	0.06	0 (0.0%)	0 (0.0%)	#DIV/0!	3,373 (4.0%)	2,760 (3.3%)	0.04
...55 - 64; n (%)	6,997 (36.5%)	6,760 (35.2%)	0.03	12,548 (60.4%)	12,685 (61.1%)	-0.01	1,434 (3.2%)	1,078 (2.4%)	0.05	20,979 (24.9%)	20,523 (24.3%)	0.01
...65 - 74; n (%)	8,588 (44.8%)	9,298 (48.5%)	-0.07	4,672 (22.5%)	5,162 (24.8%)	-0.05	34,293 (77.3%)	34,597 (78.0%)	-0.02	47,553 (56.4%)	49,057 (58.2%)	-0.04
...>=75; n (%)	2,318 (12.1%)	2,093 (10.9%)	0.04	1,468 (7.1%)	1,206 (5.8%)	0.05	8,654 (19.5%)	8,706 (19.6%)	0.00	12,440 (14.7%)	12,005 (14.2%)	0.01
Gender - United												
...Males; n (%)	9,107 (47.5%)	9,089 (47.4%)	0.00	10,509 (50.6%)	10,673 (51.4%)	-0.02	19,489 (43.9%)	19,600 (44.2%)	-0.01	39,105 (46.4%)	39,362 (46.7%)	-0.01
...Females; n (%)	10,080 (52.5%)	10,098 (52.6%)	0.00	10,268 (49.4%)	10,104 (48.6%)	0.02	24,892 (56.1%)	24,781 (55.8%)	0.01	45,240 (53.6%)	44,983 (53.3%)	0.01
Race												
...White; n (%)	N/A	N/A		N/A	N/A		38,069 (85.8%)	37,846 (85.3%)	0.01	38,069 (85.8%)	37,846 (85.3%)	0.01

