History of CABG or PTCa; n (%)	1,375 (7.2%)	1,387 (7.2%)		840 (4.0%)	825 (4.0%)		3,726 (8.4%)	3,698 (8.3%)		5,941 (7.0%)	5,910 (7.0%)	
Any stroke; n (%)	1,414 (7.4%)	1,401 (7.3%)		1,494 (7.2%)	1,500 (7.3%)		3,852 (8.7%)	3,786 (8.5%)		6,760 (8.0%)	6,687 (7.9%)	
Ischemic stroke (w and w/o mention of cerebral infarction); n (%)	1,392 (7.3%)	1,390 (7.2%)		1,476 (7.1%)	1,479 (7.1%)		3,816 (8.6%)	3,753 (8.5%)		6,684 (7.9%)	6,622 (7.9%)	
Hemorrhagic stroke; n (%)	38 (0.2%)	31 (0.2%)		37 (0.2%)	36 (0.2%)		80 (0.2%)	62 (0.1%)		155 (0.2%)	129 (0.2%)	
TIA; n (%)	328 (1.7%)	326 (1.7%)		379 (1.8%)	363 (1.7%)		848 (1.9%)	769 (1.7%)		1,555 (1.8%)	1,458 (1.7%)	0.01
Other cerebrovascular disease; n (%)	355 (1.9%)	330 (1.7%)		255 (1.2%)	237 (1.1%)		883 (2.0%)	895 (2.0%)		1,493 (1.8%)	1,462 (1.7%)	0.01
Late effects of cerebrovascular disease; n (%)	261 (1.4%)	244 (1.3%)		142 (0.7%)	150 (0.7%)		598 (1.3%)	634 (1.4%)		1,001 (1.2%)	1,028 (1.2%)	0.00
Cerebrovascular procedure; n (%)	9 (0.0%)	21 (0.1%)		24 (0.1%)	24 (0.1%)		61 (0.1%)	45 (0.1%)		994 (0.1%)	990 (0.1%)	
Heart failure (CHF); n (%)	2,017 (10.5%)	2,032 (10.6%)		1,594 (7.7%)	1,572 (7.6%)		4,950 (11.2%)	4,901 (11.0%)		8,561 (10.1%)	8,505 (10.1%)	
Peripheral Vascular Disease (PVD) or PVD Surgery ; n (%)	1,696 (8.8%)	1,705 (8.9%)		1,697 (8.2%)	1,671 (8.0%)		4,485 (10.1%)	4,556 (10.3%)		7,878 (9.3%)	7,932 (9.4%)	
Atrial fibrillation; n (%)	1,491 (7.8%)	1,541 (8.0%)		1,240 (6.0%)	1,237 (6.0%)		4,728 (10.7%)	4,771 (10.8%)		7,459 (9.0%)	7,549 (9.0%)	-0.01
Other cardiac dysrhythmia; n (%)	2,008 (10.5%)	1,993 (10.4%)		1,498 (7.2%)	1,470 (7.1%)		5,142 (11.6%)	5,106 (11.5%)		8,648 (10.3%)	8,569 (10.2%)	
Cardiac conduction disorders; n (%)	538 (2.8%)	543 (2.8%)		411 (2.0%)	425 (2.0%)		1,563 (3.5%)	1,628 (3.7%)		2,512 (3.0%)	2,596 (3.1%)	-0.01
Other CVD; n (%)	2,256 (11.8%)	2,274 (11.9%)		2,290 (11.0%)	2,252 (10.8%)		6,456 (14.5%)	6,303 (14.2%)		11,002 (13.0%)	10,829 (12.8%)	0.01
Diabetes-related complications												
Diabetic retinopathy; n (%)	1,444 (7.5%)	1,474 (7.7%)		989 (4.8%)	1,022 (4.9%)		3,663 (8.3%)	3,676 (8.3%)		6,096 (7.2%)	6,172 (7.3%)	
Diabetes with other ophthalmic manifestations; n (%)	143 (0.7%)	140 (0.7%)		678 (3.3%)	726 (3.5%)		1,377 (3.1%)	1,449 (3.3%)		2,198 (2.6%)	2,315 (2.7%)	-0.01
Retinal detachment, vitreous hemorrhage, vitrectomy; n (%)	104 (0.5%)	83 (0.4%)		102 (0.5%)	71 (0.3%)		219 (0.5%)	192 (0.4%)		425 (0.5%)	346 (0.4%)	0.01

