							31,094 (77.8%)	31,681 (79.3%)	-0.04

Table 1: Liraglutide vs DPP4i

Lab result number- BNP mean	211	206	25	34	N/A	N/A	236	240
...mean (sd)	178.05 (453.45)	112.46 (210.39)	0.19	11,349.77 (55,969.06)	98.46 (169.53)	0.28	N/A	N/A
...median [IQR]	79.90 [31.80, 158.50]	44.20 [21.62, 112.70]	0.10	72.00 [34.50, 293.25]	44.35 [16.25, 119.12]	0.00	N/A	N/A
...Missing: n (%)	18,976 (98.9%)	18,981 (98.9%)	0.00	20,752 (99.8%)	20,743 (99.8%)	0.03	N/A	N/A
Lab result number- BUN (mg/dl) mean	7,901	7,376	1,341	1,179	N/A	N/A	9,242	8,555
...mean (sd)	19.20 (8.24)	19.56 (8.24)	-0.04	424.78 (7,460.56)	689.04 (11,932.92)	-0.03	N/A	N/A
...median [IQR]	17.40 [14.00, 22.00]	18.00 [14.00, 23.00]	-0.07	17.00 [13.37, 21.00]	18.00 [14.25, 22.00]	0.00	N/A	N/A
...Missing: n (%)	11,286 (58.8%)	11,811 (61.6%)	-0.06	19,436 (93.5%)	19,598 (94.6%)	-0.03	N/A	N/A
Lab result number- Creatinine (mg/dl) mean (only 0.1 to 15 included)	8,029	7,538	1,288	1,121	N/A	N/A	9,317	8,659
...mean (sd)	1.06 (0.41)	1.04 (0.37)	0.05	1.02 (0.38)	1.01 (0.32)	0.03	N/A	N/A
...median [IQR]	0.97 [0.80, 1.21]	0.96 [0.80, 1.20]	0.03	0.96 [0.79, 1.12]	0.96 [0.80, 1.14]	0.00	N/A	N/A
...Missing: n (%)	11,158 (58.2%)	11,649 (60.7%)	-0.05	19,489 (93.8%)	19,656 (94.6%)	-0.03	N/A	N/A
Lab result number- HDL level (mg/dl) mean (only <=5000 included)	6,566	6,095	1,186	1,021	N/A	N/A	7,752	7,116
...mean (sd)	46.32 (13.75)	45.91 (13.13)	0.03	45.33 (15.96)	44.46 (13.85)	0.06	N/A	N/A
...median [IQR]	44.00 [37.00, 53.50]	44.00 [37.00, 53.00]	0.00	44.00 [36.00, 53.00]	43.00 [36.00, 52.00]	0.07	N/A	N/A
...Missing: n (%)	12,621 (65.8%)	13,092 (68.2%)	-0.05	19,591 (94.3%)	19,756 (95.1%)	-0.04	N/A	N/A
Lab result number- LDL level (mg/dl) mean (only <=5000 included)	6,629	6,170	1,149	949	N/A	N/A	7,778	7,119
...mean (sd)	85.21 (38.16)	81.93 (36.98)	0.09	84.96 (41.84)	83.77 (40.06)	0.03	N/A	N/A
...median [IQR]	82.00 [62.00, 106.50]	79.00 [60.00, 102.00]	0.08	84.00 [61.50, 108.00]	84.00 [62.00, 106.00]	0.00	N/A	N/A
...Missing: n (%)	12,558 (65.5%)	13,017 (67.8%)	-0.05	19,628 (94.5%)	19,828 (95.4%)	-0.04	N/A	N/A
Lab result number- Total cholesterol (mg/dl) mean (only <5000 included)	6,675	6,213	1,205	1,034	N/A	N/A	7,880	7,247
...mean (sd)	170.81 (45.37)	167.71 (42.55)	0.07	171.98 (53.53)	170.54 (48.18)	0.03	N/A	N/A
...median [IQR]	164.67 [141.00, 195.00]	162.00 [139.00, 191.00]	0.06	167.00 [142.00, 199.50]	166.00 [142.88, 196.00]	0.02	N/A	N/A

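### Heart-failure severity is not measured directly in the propensity score, and the one laboratory check (1.1% of matched Optum patients) shows median BNP 1.81 times as high under DPP4i

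*Combined protocol and SAP*

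**What the plan says.** Section 9 defines the matching model: "The PS should include the complete list of covariates (excluding laboratory values, which are missing in some patients"). The covariates are those of Table 1 in Appendix B.

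In that table heart failure as a diagnosis is one row, "Heart failure (CHF); n" (%), a yes/no indicator. There is no functional class, no ejection fraction, and no row that separates a heart-failure admission from an outpatient code. Several rows carry severity indirectly: loop diuretics, digoxin, sacubitril/valsartan, edema, cardiologist visits, and all-cause hospitalisation (any, last 30 days, days 31 to 180).

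Appendix A, Exclusion 7, now screens out NYHA class IV by oxygen-use codes. The superseded definition, "Inpatient Heart failure (CHF) in prior 60 days", was replaced on 4/22/2019 with a stated reason. That is a documented change, not an inconsistency.

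BNP stays out of the PS but is reported after matching. For Optum, liraglutide against DPP4i, the median and quartiles are printed as "79.90 [31.80, 158.50" (DPP4i) and "44.20 [21.62, 112.70" (liraglutide), with closing brackets cut here. The means and SDs are "178.05 (453.45" and "112.46 (210.39". Medicare has no laboratory values.

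**The concern.** A balanced yes/no row shows that equal shares carry the diagnosis. It does not show that the disease is equally advanced. Someone recently discharged after decompensated heart failure and someone with a routine clinic code contribute the same value. Under the current Exclusion 7 the former can enter unless oxygen use is coded, and no covariate marks them.

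The only direct biomarker in the balance tables differs between the matched arms, and it is higher under DPP4i. Death is part of the primary composite. If DPP4i patients do have more severe heart failure, the hazard ratio would be pushed below 1, the same direction as the trial result of 0.87 that the study hopes to reproduce. Residual confounding could then pass for replication.

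**Working it through.** **Inputs** (Appendix B, Table 1, liraglutide vs DPP4i, Optum; DPP4i first)
- Matched pairs: 19,187.
- CHF row: 2,017 (10.5%) and 2,032 (10.6%).
- BNP available, matched: 211 and 206, so (211 + 206)/38,374 = 1.1%.
- BNP mean (SD): matched 178.05 (453.45) and 112.46 (210.39); unmatched 202.08 (359.17) and 111.51 (209.59).
- BNP quartiles: matched 31.80/79.90/158.50 and 21.62/44.20/112.70; unmatched 33.40/88.65/217.10 and 20.85/43.85/111.38.

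**1. The plan's own figures.** Standardised difference = (m1 − m2)/√((s1² + s2²)/2).
- Matched means: 65.59/353.5 = 0.186, printed 0.19.
- Unmatched means: 90.57/294.1 = 0.308, printed 0.31.
- Matched medians over the same SD: 35.70/353.5 = 0.101, printed 0.10. The SD is 2.5 times the DPP4i mean, so this row understates the gap in a very skewed variable.

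**2. Ratio of matched medians.** 79.90/44.20 = 1.81. For an approximate interval, assume log-normal BNP:
- Log-SD = ln(Q3/Q1)/1.349: ln(158.50/31.80)/1.349 = 1.19 and ln(112.70/21.62)/1.349 = 1.22.
- SE of the log ratio = 1.2533 × √(1.19²/211 + 1.22²/206) = 0.148.
- 95% CI = exp(0.592 ± 1.96 × 0.148) = 1.35 to 2.42.
- Log-scale standardised difference: about 0.592/1.21 = 0.49.

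**3. What matching did.** DPP4i/liraglutide ratio at each quartile:

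| | Before | After | Share of log gap left |
|---|---|---|---|
| Lower quartile | 1.60 | 1.47 | 82% |
| Median | 2.02 | 1.81 | 84% |
| Upper quartile | 1.95 | 1.41 | 51% |

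**4. The other matched BNP medians.** Same method:
- MarketScan, DPP4i: 72.00/44.35 = 1.62 (n = 25 and 34; CI 0.60 to 4.40).
- Optum, sulfonylurea: 67.00/46.65 = 1.44 (n = 121 and 124; CI 0.90 to 2.29).
- MarketScan, sulfonylurea: 42.00/24.00 = 1.75 (n = 21 and 23; CI 0.58 to 5.25).

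All point the same way, but each interval includes 1.

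**5. Indirect markers, matched Optum.** Standardised differences computed from the counts: CHF −0.003, loop diuretics −0.012, digoxin −0.004, sacubitril/valsartan 0.003, edema −0.002, any hospitalisation −0.001, hospitalisation in the last 30 days −0.011, in days 31 to 180 0.003, any cardiologist visit −0.008.

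**6. What marginal balance leaves open.** In matched Optum, 2,017 and 2,032 patients have the CHF code, and 1,541 and 1,546 have any admission. Those margins fit any overlap from 0 to 1,541 in the DPP4i arm and from 0 to 1,546 in the liraglutide arm. This is a bound, not an estimate. It shows that balance on each row does not guarantee balance on admission with heart failure.

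**The case against.** The strongest reply is that the BNP rows cannot bear much weight. They cover 1.1% of matched Optum patients and include anyone with a result, with or without heart failure. Even if every tested patient had the diagnosis, they would be only about 10% of the CHF patients (211/2,017 and 206/2,032). Medicare supplies 44,381 of the 84,345 pairs (53%) and has no laboratory data. Meanwhile the indirect severity markers above agree within about 0.012, and admission in the last 30 days is slightly more common under liraglutide in Optum (297 against 323). All of this stands, and it limits what may be concluded.

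Four stronger readings are tempting and not supported:
- **Heart failure enters only as one code.** The row is an indicator. Appendix A lists 11 heart-failure code stems for the inclusion criterion, and the indirect markers are in the same covariate list.
- **Severity is shown to be unbalanced.** The table cannot separate severity from a different mix of tested patients or another cause such as body weight. Recorded obesity is balanced in the full matched Optum cohort (33.1% and 32.9%), but balance among tested patients is not shown.
- **Matching hardly moved the gap.** That is true at the median. The standardised difference on means fell from 0.31 to 0.19, and about half the log gap at the upper quartile closed.
- **The bias can be sized.** One could assume recent heart-failure admission in 1–3% of patients, 1.2–1.5 times as common under DPP4i, with a 3–5-fold hazard, and obtain a shift of 0.4% to 5%. The documents give none of these inputs. The upper end needs 4.5% against 3%, about 0.015 × 84,345 = 1,265 extra DPP4i patients, while all-cause admission differs by only 7,322 − 7,231 = 91.

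What the reply does not remove is step 6: no row, alone or in combination, fixes the balance of heart-failure admission.

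**Conclusion.** The point holds in limited form. The PS adjusts for heart-failure severity only through a yes/no diagnosis and indirect markers, and it has no indicator of a heart-failure admission. The single direct check shows a residual difference in Optum that is larger than chance (ratio 1.81, approximate CI 1.35 to 2.42, resting on log-normality), in a small, selected group.

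Whether this is heart-failure severity, and whether it extends to the 98.9% of Optum patients without BNP or to the other databases, is unknown. If both were so, the bias would favour liraglutide. Its size cannot be derived from the documents, and no figure should be attached to it. This is a cheap improvement to the adjustment set, not a demonstrated failure of the matching.

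**What to change.** Before any outcome analysis (the Section 13 date is still blank):

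1. Add to the PS, in all three databases, indicators for inpatient heart failure in a recent window and in the earlier part of the 180-day baseline. Use the heart-failure code list in Appendix A, with its ICD-10 mapping, and fix the window boundary in advance.
2. Rerun the matching and update the Section 9 balance tables and Section 10 power tables.
3. Report BNP by arm on the log scale, overall and within the CHF stratum, with the number tested. The stratum result would help show whether the gap lies among patients with heart failure or in who was tested.

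**Cost.** No new data are needed. Six matches are rerun (two comparisons in three databases), a few pairs may be lost, and the revised tables should go back through the review that Section 10 requires. The indicators may not remove the BNP difference. If it persists, report it as a limitation with its direction.

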## Appendix B: Liraglutide vs 2nd Generation Sulfonylureas

[figure not shown]

Figure 48: Pre-matching propensity score overlap

[figure not shown]

Figure 49: Pre-matching propensity score overlap

[figure not shown]

Figure 24: Pre-matching propensity score overlap

The c-statistics for the propensity score model, pre-matching was 0.815. The post-matching c-statistic was 0.535.

The c-statistics for the propensity score model, pre-matching was 0.811. The post-matching c-statistic was 0.538.

The c-statistics for the propensity score model, pre-matching was 0.835. The post-matching c-statistic was 0.525.

AFTER PS MATCHING

[figure not shown]

Figure 50: Post-matching propensity score overlap

[figure not shown]

Figure 50: Post-matching propensity score overlap

[figure not shown]

Figure 25: Post-matching propensity score overlap

Table 1: Liraglutide vs 2nd Generation Sulfonylureas

Unmatched									
Variable	Optum		MarketScan		Medicare		POOLED		
	Reference- 2nd Generation SU's	Exposure- Liraglutide	St. Diff.						
Number of patients	196,712	12,485	160,161	13,808	571,468	28,511	928,341	54,804	
Age									
...mean (sd)	70.45 (7.97)	65.70 (6.79)	67.63 (9.31)	62.85 (6.12)	74.52 (7.40)	70.53 (4.98)	72.47 (7.88)	67.49 (5.73)	0.72
...median (IQR)	70.00 [65.00, 76.00]	66.00 [61.00, 70.00]	65.00 [61.00, 74.00]	62.00 [60.00, 65.00]	73.00 [68.00, 79.00]	9.00 [67.00, 73.00]	70.98 (7.88)	66.55 (5.73)	0.64
Age categories									
...18 - 54; n (%)	4,772 (2.4%)	740 (5.9%)	7,998 (5.0%)	1,177 (8.5%)	0 (0.0%)	0 (0.0%)	12,770 (1.4%)	1,917 (3.5%)	-0.14
...55 - 64; n (%)	38,842 (19.7%)	4,610 (36.9%)	70,249 (43.9%)	8,602 (62.3%)	9,764 (1.7%)	694 (2.4%)	118,855 (12.8%)	13,906 (25.4%)	-0.32
...65 - 74; n (%)	93,525 (47.5%)	5,912 (47.4%)	44,191 (27.6%)	3,328 (24.1%)	313,203 (54.8%)	22,386 (78.5%)	450,919 (48.6%)	31,626 (57.7%)	-0.18
...>75; n (%)	59,573 (30.3%)	1,223 (9.8%)	37,723 (23.6%)	701 (5.1%)	248,501 (43.5%)	5,431 (19.0%)	345,797 (37.2%)	7,355 (13.4%)	0.57
Gender									
...Males; n (%)	102,630 (52.2%)	5,601 (44.9%)	91,138 (56.9%)	6,730 (48.7%)	260,001 (45.5%)	12,045 (42.2%)	453,769 (48.9%)	24,376 (44.5%)	0.09
...Females; n (%)	94,082 (47.8%)	6,884 (55.1%)	69,023 (43.1%)	7,078 (51.3%)	311,467 (54.5%)	16,466 (57.8%)	474,572 (51.1%)	30,428 (55.5%)	-0.09
Race									
...White; n (%)	N/A	N/A	N/A	N/A	439,116 (76.8%)	24,090 (84.5%)	439,116 (76.8%)	24,090 (84.5%)	-0.20
...Black; n (%)	N/A	N/A	N/A	N/A	69,514 (12.2%)	2,568 (9.0%)	69,514 (12.2%)	2,568 (9.0%)	0.10
...Asian; n (%)	N/A	N/A	N/A	N/A	19,245 (3.4%)	380 (1.3%)	19,245 (3.4%)	380 (1.3%)	0.14
...Hispanic; n (%)	N/A	N/A	N/A	N/A	22,497 (3.9%)	511 (1.8%)	22,497 (3.9%)	511 (1.8%)	0.13
...North American Native; n (%)	N/A	N/A	N/A	N/A	3,768 (0.7%)	122 (0.4%)	3,768 (0.7%)	122 (0.4%)	0.04
...Other/Unknown; n (%)	N/A	N/A	N/A	N/A	17,328 (3.0%)	840 (2.9%)	17,328 (3.0%)	840 (2.9%)	0.01
Region (lumping missing&other category with West)									
...Northeast; n (%)	21,016 (10.7%)	1,203 (9.6%)	28,601 (17.9%)	2,794 (20.2%)	94,259 (16.5%)	4,708 (16.5%)	143,876 (15.5%)	8,705 (15.9%)	-0.01
...South; n (%)	92,464 (47.0%)	6,770 (54.2%)	46,370 (29.0%)	2,793 (20.2%)	247,501 (43.3%)	13,088 (45.9%)	386,335 (41.6%)	22,651 (41.3%)	0.01
...Midwest; n (%)	38,854 (19.8%)	2,335 (18.7%)	61,418 (38.3%)	6,610 (47.9%)	138,467 (24.2%)	6,152 (21.6%)	238,739 (25.7%)	15,097 (27.5%)	-0.04
...West; n (%)	44,378 (22.6%)	2,177 (17.4%)	22,358 (14.0%)	1,452 (10.5%)	91,241 (16.0%)	4,563 (16.0%)	157,977 (17.0%)	8,192 (14.9%)	0.06
...Unknown+missing; n (%)	N/A	N/A	1,414 (0.9%)	159 (1.2%)	N/A	N/A	1,414 (0.9%)	159 (1.2%)	-0.03
CV Covariates									
Ischemic heart disease; n (%)	55,227 (28.1%)	3,702 (29.7%)	52,321 (32.7%)	4,439 (32.1%)	187,624 (32.8%)	8,905 (31.2%)	295,172 (31.8%)	17,046 (31.1%)	0.02
Acute MI; n (%)	3,262 (1.7%)	174 (1.4%)	3,103 (1.9%)	212 (1.5%)	10,813 (1.9%)	338 (1.2%)	17,178 (1.9%)	724 (1.3%)	0.05
ACS/unstable angina; n (%)	3,647 (1.9%)	261 (2.1%)	3,557 (2.2%)	286 (2.1%)	11,272 (2.0%)	482 (1.7%)	18,476 (2.0%)	1,029 (1.9%)	0.01
Old MI; n (%)	8,091 (4.1%)	491 (3.9%)	4,508 (2.8%)	292 (2.1%)	26,566 (4.6%)	1,041 (3.7%)	39,165 (4.2%)	1,824 (3.3%)	0.05
Stable angina; n (%)	7,795 (4.0%)	598 (4.8%)	5,435 (3.4%)	500 (3.6%)	21,550 (3.8%)	1,130 (4.0%)	34,780 (3.7%)	2,228 (4.1%)	-0.02
Coronary atherosclerosis and other forms of chronic									
ischemic heart disease; n (%)	51,300 (26.1%)	3,479 (27.9%)	49,443 (30.9%)	4,229 (30.6%)	178,665 (31.3%)	8,493 (29.8%)	279,408 (30.1%)	16,201 (29.6%)	0.01
Other atherosclerosis with ICD10 ; n (%)	2,423 (1.2%)	121 (1.0%)	2,102 (1.3%)	159 (1.2%)	11,227 (2.0%)	473 (1.7%)	15,752 (1.7%)	753 (1.4%)	0.02
Previous cardiac procedure (CABG or PTCA or Stent) ; n (%)	1,607 (0.8%)	96 (0.8%)	1,929 (1.2%)	140 (1.0%)	4,469 (0.8%)	143 (0.5%)	8,005 (0.9%)	379 (0.7%)	0.02
History of CABG or PTCA; n (%)	12,855 (6.5%)	921 (7.4%)	6,551 (4.1%)	579 (4.2%)	53,044 (9.3%)	2,384 (8.4%)	72,450 (7.8%)	3,884 (7.1%)	0.03
Any stroke; n (%)	16,353 (8.3%)	905 (7.2%)	15,031 (9.4%)	1,024 (7.4%)	62,700 (11.0%)	2,451 (8.6%)	94,084 (10.1%)	4,380 (8.0%)	0.07
Ischemic stroke (w and w/o mention of cerebral									
infarction); n (%)	16,102 (8.2%)	900 (7.2%)	14,822 (9.3%)	1,006 (7.3%)	61,905 (10.8%)	2,428 (8.5%)	92,829 (10.0%)	4,334 (7.9%)	0.07
Hemorrhagic stroke; n (%)	545 (0.3%)	16 (0.1%)	459 (0.3%)	28 (0.2%)	2,008 (0.4%)	45 (0.2%)	3,012 (0.3%)	89 (0.2%)	0.02
TIA; n (%)	4,010 (2.0%)	233 (1.9%)	4,022 (2.5%)	242 (1.8%)	14,808 (2.6%)	516 (1.8%)	22,840 (2.5%)	991 (1.8%)	0.05
Other cerebrovascular disease; n (%)	4,639 (2.4%)	230 (1.8%)	3,239 (2.0%)	167 (1.2%)	19,559 (3.4%)	587 (2.1%)	27,437 (3.0%)	984 (1.8%)	0.08
Late effects of cerebrovascular disease; n (%)	4,527 (2.3%)	144 (1.2%)	2,805 (1.8%)	95 (0.7%)	18,669 (3.3%)	415 (1.5%)	26,001 (2.8%)	654 (1.2%)	0.11
Cerebrovascular procedure; n (%)	288 (0.1%)	12 (0.1%)	311 (0.2%)	11 (0.1%)	935 (0.2%)	26 (0.1%)	1,534 (0.2%)	49 (0.1%)	0.03
Heart failure (CHF); n (%)	21,366 (10.9%)	1,275 (10.2%)	16,040 (10.0%)	995 (7.2%)	84,892 (14.9%)	3,352 (11.8%)	122,298 (13.2%)	5,622 (10.3%)	0.09
Peripheral Vascular Disease (PVD) or PVD Surgery ; n (%)	18,962 (9.6%)	1,095 (8.8%)	14,043 (8.8%)	1,080 (7.8%)	73,310 (12.8%)	2,955 (10.4%)	106,315 (11.5%)	5,130 (9.4%)	0.07
Atrial fibrillation; n (%)	18,759 (9.5%)	962 (7.7%)	13,972 (8.7%)	789 (5.7%)	81,612 (14.3%)	3,081 (10.8%)	114,343 (12.3%)	4,832 (8.8%)	0.11
Other cardiac dysrhythmia; n (%)	21,281 (10.8%)	1,309 (10.5%)	14,014 (8.7%)	949 (6.9%)	82,684 (14.5%)	3,363 (11.8%)	117,979 (12.7%)	5,621 (10.3%)	0.08
Cardiac conduction disorders; n (%)	6,617 (3.4%)	355 (2.8%)	4,460 (2.8%)	289 (2.1%)	28,034 (4.9%)	1,077 (3.8%)	39,111 (4.2%)	1,721 (3.1%)	0.06
Other CVD; n (%)	26,092 (13.3%)	1,498 (12.0%)	20,400 (12.7%)	1,465 (10.6%)	99,284 (17.4%)	4,174 (14.6%)	145,776 (15.7%)	7,137 (13.0%)	0.08
Diabetes-related complications									
Diabetic retinopathy; n (%)	11,089 (5.6%)	956 (7.7%)	6,538 (4.1%)	659 (4.8%)	32,274 (5.6%)	2,394 (8.4%)	49,901 (5.4%)	4,009 (7.3%)	-0.08
Diabetes with other ophthalmic manifestations; n (%)	1,424 (0.7%)	91 (0.7%)	4,704 (2.9%)	449 (3.3%)	13,704 (2.4%)	880 (3.1%)	19,832 (2.1%)	1,420 (2.6%)	-0.03
Retinal detachment, vitreous hemorrhage, vitrectomy; n (%)	717 (0.4%)	54 (0.4%)	464 (0.3%)	47 (0.3%)	1,892 (0.3%)	138 (0.5%)	3,073 (0.3%)	239 (0.4%)	-0.02
Retinal laser coagulation therapy; n (%)	944 (0.5%)	75 (0.6%)	860 (0.5%)	92 (0.7%)	2,550 (0.4%)	201 (0.7%)	4,354 (0.5%)	368 (0.7%)	-0.03
Occurrence of Diabetic Neuropathy ; n (%)	34,538 (17.6%)	2,995 (24.0%)	17,014 (10.6%)	1,961 (14.2%)	95,926 (16.8%)	6,700 (23.5%)	147,478 (15.9%)	11,656 (21.3%)	-0.14

Table 1: Liraglutide vs 2nd Generation Sulfonylureas

Occurrence of diabetic nephropathy with ICD10 ; n (%)	31,872 (16.2%)	2,161 (17.3%)	11,026 (6.9%)	1,042 (7.5%)	54,295 (9.5%)	3,539 (12.4%)	97,193 (10.5%)	6,742 (12.3%)	-0.06
Hypoglycemia ; n (%)	5,003 (2.5%)	275 (2.2%)	5,026 (3.1%)	413 (3.0%)	16,139 (2.8%)	853 (3.0%)	26,168 (2.8%)	1,541 (2.8%)	0.00
Hyperglycemia; n (%)	8,676 (4.4%)	579 (4.6%)	5,054 (3.2%)	429 (3.1%)	29,706 (5.2%)	1,240 (4.3%)	43,436 (4.7%)	2,248 (4.1%)	0.03
Disorders of fluid electrolyte and acid-base balance; n (%)	17,943 (9.1%)	827 (6.6%)	11,019 (6.9%)	607 (4.4%)	69,422 (12.1%)	2,164 (7.6%)	98,384 (10.6%)	3,598 (6.6%)	0.14
Diabetic ketoacidosis; n (%)	210 (0.1%)	14 (0.1%)	153 (0.1%)	17 (0.1%)	731 (0.1%)	33 (0.1%)	1,094 (0.1%)	64 (0.1%)	0.00
Hyperosmolar hyperglycemic nonketotic syndrome (HONK); n (%)	1,026 (0.5%)	70 (0.6%)	579 (0.4%)	44 (0.3%)	2,876 (0.5%)	128 (0.4%)	4,481 (0.5%)	242 (0.4%)	0.01
Diabetes with peripheral circulatory disorders with ICD-10 ; n (%)	15,191 (7.7%)	987 (7.9%)	6,670 (4.2%)	540 (3.9%)	42,778 (7.5%)	2,040 (7.2%)	64,639 (7.0%)	3,567 (6.5%)	0.02
Diabetic Foot; n (%)	4,860 (2.5%)	320 (2.6%)	3,959 (2.5%)	304 (2.2%)	18,615 (3.3%)	940 (3.3%)	27,434 (3.0%)	1,564 (2.9%)	0.01
Gangrene; n (%)	669 (0.3%)	34 (0.3%)	552 (0.3%)	20 (0.1%)	2,088 (0.4%)	60 (0.2%)	3,309 (0.4%)	114 (0.2%)	0.04
Lower extremity amputation; n (%)	1,382 (0.7%)	109 (0.9%)	710 (0.4%)	41 (0.3%)	4,515 (0.8%)	165 (0.6%)	6,607 (0.7%)	315 (0.6%)	0.01
Osteomyelitis; n (%)	1,371 (0.7%)	88 (0.7%)	1,120 (0.7%)	66 (0.5%)	4,379 (0.8%)	168 (0.6%)	6,870 (0.7%)	322 (0.6%)	0.01
Skin infections ; n (%)	11,149 (5.7%)	742 (5.9%)	9,819 (6.1%)	811 (5.9%)	43,277 (7.6%)	2,258 (7.9%)	64,245 (6.9%)	3,811 (7.0%)	0.00
Erectile dysfunction; n (%)	4,789 (2.4%)	360 (2.9%)	3,269 (2.0%)	318 (2.3%)	10,887 (1.9%)	833 (2.9%)	18,945 (2.0%)	1,511 (2.8%)	-0.05
Diabetes with unspecified complication; n (%)	9,112 (4.6%)	827 (6.6%)	5,419 (3.4%)	659 (4.8%)	25,116 (4.4%)	1,673 (5.9%)	39,647 (4.3%)	3,159 (5.8%)	-0.07
Diabetes mellitus without mention of complications; n (%)	174,528 (88.7%)	10,824 (86.7%)	150,098 (93.7%)	12,905 (93.5%)	539,347 (94.4%)	26,472 (92.8%)	863,973 (93.1%)	50,201 (91.6%)	0.06
Hypertension: 1 inpatient or 2 outpatient claims within 365 days; n (%)	185,514 (94.3%)	11,887 (95.2%)	139,282 (87.0%)	12,287 (89.0%)	550,194 (96.3%)	27,630 (96.9%)	874,990 (94.3%)	51,804 (94.5%)	-0.01
Hyperlipidemia ; n (%)	144,099 (73.3%)	9,851 (78.9%)	99,840 (62.3%)	9,823 (71.1%)	435,198 (76.2%)	23,633 (82.9%)	679,137 (73.2%)	43,307 (79.0%)	0.14
Edema; n (%)	14,841 (7.5%)	1,088 (8.7%)	9,129 (5.7%)	846 (6.1%)	62,616 (11.0%)	3,218 (11.3%)	86,586 (9.3%)	5,152 (9.4%)	0.00
Renal Dysfunction (non-diabetic); n (%)	50,792 (25.8%)	2,889 (23.1%)	27,130 (16.9%)	1,892 (13.7%)	141,930 (24.8%)	6,290 (22.1%)	219,852 (23.7%)	11,071 (20.2%)	0.08
Occurrence of acute renal disease; n (%)	9,401 (4.8%)	369 (3.0%)	6,016 (3.8%)	216 (1.6%)	35,473 (6.2%)	909 (3.2%)	50,890 (5.5%)	1,494 (2.7%)	0.14
Occurrence of chronic renal insufficiency; n (%)	42,651 (21.7%)	2,481 (19.9%)	19,946 (12.5%)	1,449 (10.5%)	116,950 (20.5%)	5,396 (18.9%)	179,547 (19.3%)	9,326 (17.0%)	0.06
Chronic kidney disease ; n (%)	41,223 (21.0%)	2,405 (19.3%)	19,353 (12.1%)	1,392 (10.1%)	111,247 (19.5%)	5,116 (17.9%)	171,823 (18.5%)	8,913 (16.3%)	0.06
CKD Stage 3-4; n (%)	29,293 (14.9%)	1,735 (13.9%)	13,900 (8.7%)	1,030 (7.5%)	76,878 (13.5%)	3,680 (12.9%)	120,071 (12.9%)	6,445 (11.8%)	0.03
Occurrence of hypertensive nephropathy; n (%)	18,774 (9.5%)	1,084 (8.7%)	8,031 (5.0%)	535 (3.9%)	56,974 (10.0%)	2,269 (8.0%)	83,779 (9.0%)	3,888 (7.1%)	0.07
Occurrence of miscellaneous renal insufficiency ; n (%)	12,325 (6.3%)	641 (5.1%)	7,652 (4.8%)	513 (3.7%)	45,632 (8.0%)	1,823 (6.4%)	65,609 (7.1%)	2,977 (5.4%)	0.07
Glaucoma or cataracts ; n (%)	41,679 (21.2%)	2,571 (20.6%)	28,496 (17.8%)	2,350 (17.0%)	144,998 (25.4%)	8,094 (28.4%)	215,173 (23.2%)	13,015 (23.7%)	-0.01
Cellulitis or abscess of toe; n (%)	2,852 (1.4%)	189 (1.5%)	1,698 (1.1%)	126 (0.9%)	9,051 (1.6%)	446 (1.6%)	13,601 (1.5%)	761 (1.4%)	0.01
Foot ulcer; n (%)	4,802 (2.4%)	302 (2.4%)	4,015 (2.5%)	304 (2.2%)	18,697 (3.3%)	921 (3.2%)	27,514 (3.0%)	1,527 (2.8%)	0.01
Bladder stones; n (%)	269 (0.1%)	8 (0.1%)	223 (0.1%)	14 (0.1%)	1,039 (0.2%)	41 (0.1%)	1,531 (0.2%)	63 (0.1%)	0.03
Kidney stones; n (%)	4,100 (2.1%)	318 (2.5%)	3,487 (2.2%)	341 (2.5%)	14,180 (2.5%)	805 (2.8%)	21,767 (2.3%)	1,464 (2.7%)	-0.03
Urinary tract infections (UTIs); n (%)	19,351 (9.8%)	1,136 (9.1%)	11,757 (7.3%)	940 (6.8%)	84,914 (14.9%)	3,659 (12.8%)	116,022 (12.5%)	5,735 (10.5%)	0.06
Dipstick urinalysis; n (%)	68,120 (34.6%)	4,493 (36.0%)	46,700 (29.2%)	4,559 (33.0%)	223,752 (39.2%)	11,639 (40.8%)	338,572 (36.5%)	20,691 (37.8%)	-0.03
Non-dipstick urinalysis; n (%)	76,422 (38.8%)	5,479 (43.9%)	42,377 (26.5%)	4,897 (35.5%)	205,498 (36.0%)	13,140 (46.1%)	324,297 (34.9%)	23,516 (42.9%)	0.16
Urine function test; n (%)	4,806 (2.4%)	280 (2.2%)	4,075 (2.5%)	345 (2.5%)	17,903 (3.1%)	986 (3.5%)	26,784 (2.9%)	1,611 (2.9%)	0.00
Cytology; n (%)	1,477 (0.8%)	85 (0.7%)	1,544 (1.0%)	115 (0.8%)	5,802 (1.0%)	288 (1.0%)	8,823 (1.0%)	488 (0.9%)	0.01
Cystos; n (%)	2,368 (1.2%)	147 (1.2%)	2,245 (1.4%)	176 (1.3%)	8,292 (1.5%)	418 (1.5%)	12,905 (1.4%)	741 (1.4%)	0.00
Other Covariates							#VALUE!	000 (0.0%)	#VALUE!
Liver disease; n (%)	0 (0.0%)	0 (0.0%)	0 (0.0%)	0 (0.0%)	0 (0.0%)	0 (0.0%)			
Osteoarthritis; n (%)	33,853 (17.2%)	2,542 (20.4%)	21,855 (13.6%)	2,219 (16.1%)	136,870 (24.0%)	7,450 (26.1%)	192,578 (20.7%)	12,211 (22.3%)	-0.04
Other arthritis, arthropathies and musculoskeletal pain; n (%)	71,081 (36.1%)	5,138 (41.2%)	53,785 (33.6%)	5,188 (37.6%)	259,992 (45.5%)	13,940 (48.9%)	384,858 (41.5%)	24,266 (44.3%)	-0.06
Dorsopathies; n (%)	41,440 (21.1%)	3,364 (26.9%)	30,075 (18.8%)	3,095 (22.4%)	150,059 (26.3%)	8,971 (31.5%)	221,574 (23.9%)	15,430 (28.2%)	-0.10
Fractures; n (%)	6,554 (3.3%)	371 (3.0%)	5,196 (3.2%)	351 (2.5%)	26,453 (4.6%)	1,070 (3.8%)	38,203 (4.1%)	1,792 (3.3%)	0.04
Falls; n (%)	7,893 (4.0%)	372 (3.0%)	2,427 (1.5%)	138 (1.0%)	31,012 (5.4%)	971 (3.4%)	41,332 (4.5%)	1,481 (2.7%)	0.10
Osteoporosis; n (%)	10,537 (5.4%)	556 (4.5%)	5,586 (3.5%)	427 (3.1%)	44,053 (7.7%)	2,028 (7.1%)	60,176 (6.5%)	3,011 (5.5%)	0.04
Hyperthyroidism; n (%)	1,325 (0.7%)	102 (0.8%)	756 (0.5%)	72 (0.5%)	5,224 (0.9%)	285 (1.0%)	7,305 (0.8%)	459 (0.8%)	0.00
Hypothyroidism; n (%)	29,473 (15.0%)	2,544 (20.4%)	16,299 (10.2%)	2,095 (15.2%)	84,955 (14.9%)	5,114 (17.9%)	130,727 (14.1%)	9,753 (17.8%)	0.10
Other disorders of thyroid gland ; n (%)	5,691 (2.9%)	690 (5.5%)	3,833 (2.4%)	717 (5.2%)	19,904 (3.5%)	1,782 (6.3%)	29,428 (3.2%)	3,189 (5.8%)	0.13
Depression; n (%)	15,620 (7.9%)	1,336 (10.7%)	10,206 (6.4%)	1,173 (8.5%)	65,406 (11.4%)	3,664 (12.9%)	91,232 (9.8%)	6,173 (11.3%)	-0.05
Anxiety; n (%)	12,813 (6.5%)	1,186 (9.5%)	6,953 (4.3%)	770 (5.6%)	50,865 (8.9%)	2,569 (9.0%)	70,631 (7.6%)	4,525 (8.3%)	-0.03
Sleep_Disorder; n (%)	12,444 (6.3%)	1,304 (10.4%)	13,885 (8.7%)	2,243 (16.2%)	49,765 (8.7%)	3,988 (14.0%)	76,094 (8.2%)	7,535 (13.7%)	0.18
Dementia; n (%)	10,450 (5.3%)	258 (2.1%)	6,100 (3.8%)	146 (1.1%)	54,395 (9.5%)	1,006 (3.5%)	70,945 (7.6%)	1,410 (2.6%)	0.23
Delirium; n (%)	3,084 (1.6%)	93 (0.7%)	2,269 (1.4%)	69 (0.5%)	16,516 (2.9%)	351 (1.2%)	21,869 (2.4%)	513 (0.9%)	0.12
Psychosis; n (%)	2,498 (1.3%)	81 (0.6%)	1,727 (1.1%)	57 (0.4%)	15,982 (2.8%)	256 (0.9%)	20,207 (2.2%)	394 (0.7%)	0.13
Obesity; n (%)	31,831 (16.2%)	4,320 (34.6%)	16,930 (10.6%)	3,086 (22.3%)	77,359 (13.5%)	7,939 (27.8%)	126,120 (13.6%)	15,345 (28.0%)	0.36
Overweight; n (%)	9,079 (4.6%)	534 (4.3%)	2,442 (1.5%)	267 (1.9%)	17,903 (3.1%)	820 (2.9%)	29,424 (3.2%)	1,621 (3.0%)	0.01
Smoking; n (%)	20,336 (10.3%)	1,403 (11.2%)	8,760 (5.5%)	632 (4.6%)	77,008 (13.5%)	3,563 (12.5%)	106,104 (11.4%)	5,598 (10.2%)	0.04
Alcohol abuse or dependence; n (%)	1,443 (0.7%)	47 (0.4%)	840 (0.5%)	38 (0.3%)	4,133 (0.7%)	97 (0.3%)	6,416 (0.7%)	182 (0.3%)	0.06
Drug abuse or dependence; n (%)	0 (0.0%)	0 (0.0%)	0 (0.0%)	0 (0.0%)	0 (0.0%)	0 (0.0%)	#VALUE!	00 (0.0%)	#VALUE!
COPD; n (%)	17,677 (9.0%)	1,036 (8.3%)	10,715 (6.7%)	671 (4.9%)	76,066 (13.3%)	3,280 (11.5%)	104,458 (11.3%)	4,987 (9.1%)	0.07

Table 1: Liraglutide vs 2nd Generation Sulfonylureas

Asthma; n (%)	9,916 (5.0%)	930 (7.4%)	6,975 (4.4%)	821 (5.9%)	37,105 (6.5%)	2,443 (8.6%)	53,996 (5.8%)	4,194 (7.7%)	-0.08
Obstructive sleep apnea; n (%)	14,202 (7.2%)	2,283 (18.3%)	12,619 (7.9%)	2,406 (17.4%)	38,734 (6.8%)	4,306 (15.1%)	65,555 (7.1%)	8,995 (16.4%)	-0.29
Pneumonia; n (%)	5,880 (3.0%)	256 (2.1%)	4,981 (3.1%)	241 (1.7%)	28,237 (4.9%)	795 (2.8%)	39,098 (4.2%)	1,292 (2.4%)	0.10
Imaging; n (%)	349 (0.2%)	15 (0.1%)	247 (0.2%)	10 (0.1%)	1,541 (0.3%)	34 (0.1%)	2,137 (0.2%)	59 (0.1%)	0.03
Diabetes Medications									
DM Medications - AGIs; n (%)	658 (0.3%)	40 (0.3%)	522 (0.3%)	48 (0.3%)	2,010 (0.4%)	121 (0.4%)	3,190 (0.3%)	209 (0.4%)	-0.02
DM Medications - Glitazones; n (%)	16,520 (8.4%)	1,216 (9.7%)	17,287 (10.8%)	1,827 (13.2%)	37,921 (6.6%)	2,572 (9.0%)	71,728 (7.7%)	5,615 (10.2%)	-0.09
DM Medications - Insulin; n (%)	11,363 (5.8%)	2,682 (21.5%)	9,783 (6.1%)	2,740 (19.8%)	40,963 (7.2%)	7,037 (24.7%)	62,109 (6.7%)	12,459 (22.7%)	-0.46
DM Medications - Meglitinides; n (%)	1,281 (0.7%)	146 (1.2%)	1,525 (1.0%)	311 (2.3%)	5,854 (1.0%)	590 (2.1%)	8,660 (0.9%)	1,047 (1.9%)	-0.09
DM Medications - Metformin; n (%)	125,476 (63.8%)	7,325 (58.7%)	100,419 (62.7%)	8,570 (62.1%)	355,150 (62.1%)	17,242 (60.5%)	581,045 (62.6%)	33,137 (60.5%)	0.04
Concomitant initiation or current use of SGLT2i; n (%)	2,699 (1.4%)	717 (5.7%)	1,961 (1.2%)	731 (5.3%)	4,774 (0.8%)	1,220 (4.3%)	9,434 (1.0%)	2,668 (4.9%)	-0.23
Concomitant initiation or current use of AGIs; n (%)	472 (0.2%)	22 (0.2%)	391 (0.2%)	29 (0.2%)	1,434 (0.3%)	83 (0.3%)	2,297 (0.2%)	134 (0.2%)	0.00
Concomitant initiation or current use of Glitazones; n (%)	12,440 (6.3%)	873 (7.0%)	12,991 (8.1%)	1,304 (9.4%)	28,770 (5.0%)	1,961 (6.9%)	54,201 (5.8%)	4,138 (7.6%)	-0.07
Concomitant initiation or current use of DPP4i ; n (%)	4,204 (2.1%)	109 (0.9%)	4,943 (3.1%)	124 (0.9%)	13,128 (2.3%)	225 (0.8%)	22,275 (2.4%)	#VALUE!	#VALUE!
Concomitant initiation or current use of Insulin; n (%)	6,048 (3.1%)	1,683 (13.5%)	5,661 (3.5%)	1,712 (12.4%)	22,161 (3.9%)	4,433 (15.5%)	33,870 (3.6%)	7,828 (14.3%)	-0.38
Concomitant initiation or current use of Meglitinides; n (%)	781 (0.4%)	86 (0.7%)	931 (0.6%)	215 (1.6%)	3,651 (0.6%)	402 (1.4%)	5,363 (0.6%)	703 (1.3%)	-0.07
Concomitant initiation or current use of Metformin; n (%)	105,292 (53.5%)	5,852 (46.9%)	83,840 (52.3%)	6,810 (49.3%)	296,366 (51.9%)	13,865 (48.6%)	485,498 (52.3%)	26,527 (48.4%)	0.08
Past use of SGLT2i ; n (%)	1,362 (0.7%)	294 (2.4%)	795 (0.5%)	249 (1.8%)	2,664 (0.5%)	540 (1.9%)	4,821 (0.5%)	1,083 (2.0%)	-0.14
Past use of AGIs; n (%)	186 (0.1%)	18 (0.1%)	131 (0.1%)	19 (0.1%)	576 (0.1%)	38 (0.1%)	893 (0.1%)	75 (0.1%)	0.00
Past use of Glitazones ; n (%)	4,080 (2.1%)	343 (2.7%)	4,296 (2.7%)	523 (3.8%)	9,151 (1.6%)	611 (2.1%)	17,527 (1.9%)	1,477 (2.7%)	-0.05
Past use of DPP4i ; n (%)	4,798 (2.4%)	474 (3.8%)	4,852 (3.0%)	747 (5.4%)	17,036 (3.0%)	1,321 (4.6%)	26,686 (2.9%)	2,542 (4.6%)	-0.09
Past use of Insulin ; n (%)	5,316 (2.7%)	999 (8.0%)	4,122 (2.6%)	1,028 (7.4%)	18,807 (3.3%)	2,604 (9.1%)	28,245 (3.0%)	4,631 (8.5%)	-0.24
Past use of Meglitinides ; n (%)	500 (0.3%)	60 (0.5%)	594 (0.4%)	96 (0.7%)	2,203 (0.4%)	188 (0.7%)	3,297 (0.4%)	344 (0.6%)	-0.03
Past use of metformin (final) ; n (%)	20,184 (10.3%)	1,473 (11.8%)	16,579 (10.4%)	1,760 (12.7%)	58,784 (10.3%)	3,377 (11.8%)	95,547 (10.3%)	6,610 (12.1%)	-0.06
Other Medications									
Use of ACE inhibitors; n (%)	95,481 (48.5%)	5,189 (41.6%)	75,829 (47.3%)	5,623 (40.7%)	267,223 (46.8%)	11,669 (40.9%)	438,533 (47.2%)	22,481 (41.0%)	0.13
Use of ARBs; n (%)	50,472 (25.7%)	4,265 (34.2%)	43,683 (27.3%)	5,149 (37.3%)	155,237 (27.2%)	10,277 (36.0%)	249,392 (26.9%)	19,691 (35.9%)	-0.19
